10.3.2 Stopping Criteria

10.3.3 General Stopping Criteria

The study will be discontinued if any unacceptable safety findings are identified. This decision will be made jointly by the Principal Investigator (or deputy) and the Sponsor. A written document signed by the Principal Investigator (or deputy) and Sponsor will be produced ratifying the decision.

Individual participants may also be withdrawn for any of the reasons outlined in [Section 10.7.4](#).

10.3.4 Progression from Dose Leader Group/Dose Escalation Stopping Criteria

If any of the below-listed criteria are met, further dosing or dose escalation between cohorts will be temporarily stopped pending evaluation of all available data:

- ‘serious’ adverse reaction (i.e., a serious adverse event considered related to the IMP administration) in one participant, as defined in [Section 10.9.11](#).
- ‘severe’ non-serious adverse reactions (i.e., severe non-serious adverse events considered related to the IMP administration) in two participants in the same cohort, independent of within or not within the same system-organ-class, as defined in [Section 10.9.11](#).
- 4 out of 8 participants in a cohort experience the same moderate or severe AE that is considered related to the IMP.
- 1 or more participant in the cohort experiences a drug related SAE.
- Any participant experiences a severe AE in any key safety variable (ECG, laboratory safety or vital signs) that in the opinion of the Investigator is at least possibly related to the IMP and may jeopardise the safety of the participants.
- QTcF < 330 ms, QTcF > 500 ms or a QTcF increase of > 60 ms in any participant confirmed on 3 consecutive ECGs, at least 1 min a part.
- Systemic exposure (C_{max} and AUC) for a dose that is anticipated to exceed pre-determined exposure limits based on preclinical toxicology data and/or already available human PK data i.e., $C_{max} = 3.26 \mu\text{g}/\text{mL}$ & $AUC_{0-24} = 14.859 \mu\text{g}^*\text{h}/\text{mL}$.
- Any other toxicity which in the opinion of the Principal Investigator and the medical monitors of CRO and Sponsor would preclude dosing additional participants at the indicated dose level.
- Any of the following elevation in a liver function test result, must have a possible relationship to IMP, to be confirmed on repeat samples, and other potential causes (i.e., strenuous exercise, use of a concomitant medication, viral infection such as hepatitis A or cytomegalovirus) must have been excluded.
 - ALT or AST >3x ULN and (BIL-T >2x ULN or INR >1.5) *
 - ALT or AST >3x ULN with the appearance of fatigue, nausea, vomiting, right upper quadrant pain or tenderness, fever, rash, and/or eosinophilia (>5%) *

**Dependent on availability of liver function test data, observation may be made following progression from dose leader group. Any findings and impact will be reviewed and implemented (where applicable) immediately.*

Individual participants may also be withdrawn for any of the reasons outlined in [Section 10.7.4](#).

If any of the above criteria are fulfilled, dose escalation will only proceed once an appropriate substantial amendment has been submitted and receives regulatory approval from the MHRA and approval from the REC associated with the study.

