| Height/Weight/BMI ³ | X | X | | | | | | | | | | | | | | | | |
| Medical History & Concurrent Conditions | X | | | | | | | | | | | | | | | | | |
| Virology Tests (HIV, HBsAg, HCV) | X | | | | | | | | | | | | | | | | | |
| Drug and Alcohol Screen ⁴ | X | X | | | | | | | | | | | | | | | | |
| COVID-19 Test | | X | | | | | | | | | | | | | | X ¹⁵ | | |
| Biochemistry | X ⁷ | X ^{7,8} | | | | | | | | | | X ^{7,8} | | | X | X ⁶ | X | |
| Haematology | X | X | | | | | | | | | | X | | | X | X ⁶ | X | |
| Urinalysis | X | X | | | | | | | | | X | X | | | X | X ⁶ | X | |
| Coagulation ⁵ | X | X | | | | | | | | | X | | | | X | X ⁶ | X | |
| Randomisation | | X | | | | | | | | | | | | | | | | |
| Adverse Events | X | X | X | X | X | X | X | X | X | X | X | X | X | X | X | X | X | |
| Vital Signs ⁹ | X | X | X | | X | X | X | X | X | X | X | X | X | X | X | X ⁶ | X | |
| Physical Examination | X | X ¹³ | | | | | | | | | | | | | X ¹³ | | X ¹³ | |
| 12-Lead ECG ¹⁰ | X | X | X | | X | | | | X | | | X | X | | X | X | X ⁶ | X |
| Prior and Concomitant Medication | X | X | X | X | X | X | X | X | X | X | X | X | X | X | X | X | X | |
| Dose IMP ¹¹ | | | X | | | | | | | | | X | | X | X | X | | |
| Blood Sampling for PK | | | X | | X | X | X | X | X | X | X | X | X | X | X | X ¹⁴ | | |

| Visits ¹ | Screening | In-house | | | | | | | | | | | | | | Follow up | | | |
|-----------------------|----------------|----------|----------------------------------|--------|-----|------|----|----|----|----|----|----|-----|-----|-----|-----------|-----------------------------|--|--|
| Days | Day - 28 to -2 | Day - 1 | Day 1-4, Day 10-13 ¹⁵ | | | | | | | | | | | | | Day 5-9 | 5-7 days from last IMP dose | | |
| Time (h) | | | Pre-Dose | 0 | 0.5 | 0.75 | 1h | 2h | 3h | 4h | 6h | 8h | 12h | 24h | 36h | 48h | 72h | | |
| Urine Sampling for PK | | | X ¹² | ←————→ | | | | | | | | | | | | | | | |
| Exploratory PD sample | | | X ¹⁶ | | | | | | | | | | | | | | | | |

Study Flow Chart Footnotes:

| | |
|----|---|
| 1 | For each cohort participants will be in the clinical unit for their inpatient visit from the morning before dosing (Day -1), until the completion of all assessments on Day 13. |
| 2 | Eligibility will be determined during screening. Continued eligibility will be confirmed on Day -1, and pre-dose Day 1-10 |
| 3 | Height measured at Screening only. |
| 4 | A urine sample will be used to screen for drugs of abuse (including alcohol and cotinine). |
| 5 | Coagulation testing aPTT and PT |

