10.9.13 Grades of Adverse Event Severity

The following grades will be used by an Investigator to describe the severity of AEs.

The following are the only grades, which will be used to describe AE severity. Only 1 severity grade will be used for each AE (e.g., mild - moderate is not acceptable).

| SEVERITY OF THE AE | DEFINITION |
|--------------------|---|
| Mild | The AE does not interfere with the participant's daily routines. It causes no more than slight discomfort or mild objective change in any of the safety parameters assessed during the study as determined by the Investigator. |
| Moderate | The AE interferes with some aspects of the participant's daily routines or moderate objective change in any of the safety parameters assessed during the study as determined by the Investigator. |
| Severe | The AE causes inability to carry out the participant's daily routine or severe objective change in any of the safety parameters assessed during the study as determined by the Investigator. |

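### The liver stopping criterion in protocol 10.3.4 is met only after repeat confirmation and exclusion of other causes, with no time set for the repeat, so no automatic liver hold covers the work-up

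*Protocol*

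**What the plan says.** Protocol 10.3.4 opens with a stop-first rule: "If any of the below-listed criteria are met, further dosing or dose escalation between cohorts will be temporarily stopped", with evaluation of the data to follow.

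The liver bullet works in a different order. It has two thresholds:
- ALT or AST above 3x ULN with total bilirubin above 2x ULN or INR above 1.5;
- ALT or AST above 3x ULN with listed symptoms or eosinophilia.

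For either to count, the elevation "must have a possible relationship to IMP, to be confirmed on repeat samples, and other potential causes" have to be dealt with as well. The examples given are exercise, another medicine and infection, and the wording on infection is "viral infection such as hepatitis A or cytomegalovirus) must have been excluded".

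A footnote to both thresholds accepts that liver results may arrive after the rest of the cohort has started, and adds: "Any findings and impact will be reviewed and implemented (where applicable) immediately".

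No interval for the repeat sample appears in 10.3.4, in the AE follow-up text (10.9.16) or in the laboratory section (10.9.18). By contrast, the QTcF criterion in the same list fixes both the number of repeats and their minimum spacing (three ECGs, 1 minute). Planned virology (10.9.5) covers hepatitis B, hepatitis C and HIV only.

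**The concern.** Read literally, the liver criterion acts after the work-up, whereas the section's lead sentence stops first and evaluates afterwards. Excluding hepatitis A or cytomegalovirus needs tests outside the planned virology, and until they are back the criterion is not met. A confirmed, possibly related ALT or AST above 3x ULN with bilirubin above 2x ULN would then not, through this bullet, hold anyone's next dose. Nor would it bring in the substantial-amendment requirement at the end of 10.3.4.

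The wording applies to every part of the study, but Part C gives a dose each day for 10 days in a first-in-human setting. Each day of work-up can therefore mean one more dose for the rest of the cohort.

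**Working it through.** The plan gives no figure to reproduce. The check has two steps: which rules can act before the work-up ends, and how many doses fit into the gap.

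**Step 1. Rules that can act during the work-up**

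| Route | Where | What it needs |
|---|---|---|
| Severe laboratory AE in one participant | 10.3.4; severity in 10.9.13 | Investigator grades a "severe objective change in any of the safety parameters assessed during the study as determined by the Investigator", and it is one "that in the opinion of the Investigator is at least possibly related to the IMP and may jeopardise the safety of the participants" |
| Related SAE | 10.3.4; 10.9.15 | Event meets a seriousness criterion, which includes medical significance |
| Other toxicity | 10.3.4 | "Any other toxicity which in the opinion of the Principal Investigator and the medical monitors" would rule out further dosing at that level |
| Liver footnote | 10.3.4 | Immediate review and action where applicable; names no hold |
| Unacceptable findings | 10.3.3 | Joint decision of Principal Investigator and Sponsor |
| Individual withdrawal | 10.7.4 | Health considered compromised; that participant only |
| Dose-leader gate | 10.1 | Acceptable leader profile; governs only the start of dosing in the remainder |

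None of these routes needs a repeat sample or the exclusion of causes. All rest on judgement, and none says that reaching the liver thresholds holds dosing. The dose-leader gate can be passed before liver results are known, as the footnote accepts.

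The affected participant may be covered separately. Table 10.9.3 footnote 2 says "Continued eligibility will be confirmed on Day -1, and pre-dose Day 1-10", inclusion criterion 7 caps ALT and AST at 1.5x ULN, and 10.5 allows no deviations. However, 10.5.1 places re-confirmation on Day -1 or before the first dose, so it is uncertain whether this bars him. It does nothing for the other seven.

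**Step 2. Doses that fit into the gap (Part C, once daily, 10 days)**

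Inputs:
- Biochemistry draws during dosing: Days 2 and 4 (24 h and 72 h after the first dose) and Day 7 pre-dose in protocol V4.0, Table 10.9.3; Days 2, 4 and 5 in SAP 11.6.2.
- Work-up time w, in days from the draw. The documents do not give it, so a range is shown.
- Convention: each draw precedes that day's dose, that dose is given, and the criterion is met w days after the draw, before that day's dose. No judgement route is used.

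Further doses = min(w - 1, 10 - s), where s is the other participant's study day on the draw date. For others in the same dosing group, s is the draw day.

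| Draw | w = 1 | w = 2 | w = 3 | w = 4 | Maximum |
|---|---|---|---|---|---|
| Day 2 | 0 | 1 | 2 | 3 | 10 - 2 = 8 (w of 9 or more) |
| Day 4 | 0 | 1 | 2 | 3 | 10 - 4 = 6 (w of 7 or more) |
| Day 5 (SAP) | 0 | 1 | 2 | 3 | 10 - 5 = 5 (w of 6 or more) |
| Day 7 (V4.0) | 0 | 1 | 2 | 3 | 10 - 7 = 3 (w of 4 or more) |

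If the dose leaders run exactly one day ahead, the maximum is one higher for the later six when a leader triggers, and one lower for the leaders when a later participant triggers.

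**The case against.** The strongest reply is that the protocol is not silent. One severe, possibly related laboratory AE stops further dosing with no repeat sample. A related SAE or the other-toxicity bullet does the same. The liver footnote covers findings whether or not confirmed, and asks for immediate action. Each out-of-range result must be judged for clinical significance (10.9.18). In a residential unit, it is unlikely that all of these would go unused after ALT above 3x ULN with raised bilirubin. This stands. A reader might infer from the liver bullet that no rule can stop the rest of a cohort before the work-up ends, or that dosing must continue until then. The documents support neither reading.

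A second reply is that stopping a whole cohort on one unconfirmed value is a trade-off. The participant may be on placebo (2 of 8), confirmation is also required for QTcF, and skipped doses damage the PK analyses. This also stands: the documents do not show that a cohort-wide hold on a first result is required.

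A third reply is that the text may be superseded. The SAP is written to protocol V5.0 (15 March 2022), which is not available here. Part C laboratory monitoring did change: the SAP adds INR and moves the mid-course draw to Day 5. Whether 10.3.4 changed is unknown.

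None of these replies supplies a repeat interval or a hold linked to the liver thresholds.

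**Conclusion.** The concern holds in a limited form. The liver criterion in 10.3.4 is met only after confirmation and completed exclusion of other causes, no time is set for the repeat, and no automatic, threshold-based hold applies in between. Interim protection rests on judgement.

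The exposure at stake for others in the same dosing group is at most 8, 6 or 3 further doses after a Day 2, 4 or 7 draw (V4.0), or 5 after a Day 5 draw (SAP). These maxima assume a slow work-up and that no judgement route is used, so they are limits and not expectations. At a work-up of two days the figure is one dose.

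The event should be rare in volunteers screened to ALT and AST at or below 1.5x ULN, which also limits the expected benefit of a change. This is a cheap improvement of low-to-moderate priority.

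**What to change.** First check whether protocol V5.0 keeps this wording. If it does, state in 10.3.4:

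1. A first result at the existing liver thresholds, with a possible relationship to the IMP, holds that participant's dosing. An unscheduled repeat is taken at once, with the result sought before the next scheduled dose.
2. If the repeat does not confirm, dosing resumes.
3. If it confirms, further dosing of the cohort is held while other causes are investigated. Their exclusion then decides between restart and the criterion being fulfilled, in which case the substantial-amendment rule applies. It is no longer a precondition for the hold.

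Whether to hold the rest of the cohort on the unconfirmed first result stays with the Principal Investigator and Sponsor. Thresholds and scheduled tests do not change. For the other participants, the time to a confirmed repeat replaces w in the formula: none of them receives a further dose if a confirming result is back before the next dose, and at most one if it takes a day longer.

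The cost is one unscheduled sample per event, which Table 10.9.6 footnote 2 foresees, and possible skipped doses. No laboratory turnaround is documented and 10.9.18 allows a referral laboratory, so a late repeat is possible.
- One participant held: at most 1 of 3 x 6 = 18 planned AX-158 participants (6%) leaves the Day 10 proportionality and independence analysis, because SAP 6.3 requires all doses. On a strict reading of the evaluability definition in 10.3.1, 7 of 8 remain evaluable against the 6 needed.
- Cohort held after confirmation: up to 6 of 18 (33%) leave that analysis. The dose level's steady-state and accumulation estimates can be affected, and evaluable numbers could fall below 6. If no stopping criterion is then fulfilled, 10.8.9 allows the level to be repeated in one of the two optional cohorts.

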| | | • HED | human equivalent dose |

| | | | |
|------------|---|---------------|--|
| • HIV | human immunodeficiency virus | • Na | sodium |
| • HRA | Health Research Authority | • NCE | new chemical entity |
| • IB | Investigator's Brochure | • NHS | National Health Service |
| • ICF | informed consent form | • NOAEL | no-observed-adverse-effect level |
| • ICH | International Council on Harmonisation | • NRES | National Research Ethics Committee |
| • IMP | investigational medicinal product(s) | • PBMC | peripheral blood mononuclear cell |
| • INR | international normalised ratio | • PCH | Prince Charles Hospital |
| • ISF | Investigator site file | • PCE | polychromatic erythrocytes |
| • IUD | intrauterine device(s) | • PD | pharmacodynamic |
| • IUS | intrauterine system | • PK | pharmacokinetic |
| • K | potassium | • PPE | personal protective equipment |
| • k_{el} | elimination rate constant | • PT | prothrombin time |
| • LC MS/MS | liquid chromatography tandem mass spectrometry | • PR interval | time the electrical impulse takes to travel from the sinus node through the AV node and entering the ventricles; measured from the beginning of the P wave to the beginning of the QRS complex |
| • LFT | lateral flow test | • PV | pharmacovigilance |
| • LH | luteinising hormone | • QC | quality control |
| • LLOQ | lower limit of quantification | • QD | Once a day |
| • Ltd | Limited | • QP | qualified person |
| • MAD | Multiple Ascending dose | • QRS | QRS complex represents ventricular depolarisation |
| • MCH | mean corpuscular haemoglobin | • QT interval | the time for both ventricular depolarisation and repolarisation to occur, and therefore roughly estimates the duration of an average ventricular action potential. |
| • MCHC | mean corpuscular haemoglobin concentration | • QTc | corrected QT interval |
| • MCV | mean corpuscular volume | • QTcF | corrected QT interval using Fridericia's formula |
| • MedDRA | Medical Dictionary for Regulatory Activities | • R^2 | coefficient of determination |
| • m | metre(s) | • RBC | red blood cell(s) |
| • MHRA | Medicines and Healthcare products Regulatory Agency | • RDW | red blood cell distribution width |
| • mg | milligram(s) | • REC | Research Ethics Committee |
| • mL | millilitre(s) | • RR interval | the time elapsed between two successive R waves |
| • min | minute | | |
| • mmHg | millimetre(s) of mercury | | |
| • ms | millisecond(s) | | |
| • MRSD | maximum recommended starting dose | | |

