| Adverse Events | X | X | X | X | X | X | X | X | X | X | X | X | X | X | X | X | X |
| Vital Signs ⁸ | X | X | X | | X | X | X | X | X | X | X | X | X | X | X | X | X |
| Physical Examination | X | X ¹¹ | | | | | | | | | | | | | | X ¹¹ | X ¹¹ |
| 12-Lead ECG ⁹ | X | X | X | | X | | | | X | | | X | X | | X | X | X |

| Visits ^{1,2} | Screening | Treatment Period | | | | | | | | | | | | | | Follow up | |
|--------------------------------|----------------|------------------|-----------------|---|-----|------|----|----|----|----|----|----|--------------------------|--------------------------|--------------------------|-----------------------------|-----|
| | | In-house | | | | | | | | | | | | | | | |
| Days | Day – 28 to -2 | Day -1 | Day 1 | | | | | | | | | | Post-Treatment 1 (Day 2) | Post-Treatment 2 (Day 3) | Post-Treatment 3 (Day 4) | 5-7 days from last IMP dose | |
| Time (h) | | | Pre-Dose | 0 | 0.5 | 0.75 | 1h | 2h | 3h | 4h | 6h | 8h | 12h | 24h | 36h | 48h | 72h |
| Prior & Concomitant Medication | X | X | X | X | X | X | X | X | X | X | X | X | X | X | X | X | X |
| Dose IMP ¹⁰ | | | X | | | | | | | | | | | | | | |
| Blood Sampling for PK | | | X | | X | X | X | X | X | X | X | X | X | X | X | X | |
| Exploratory PD sample | | | X ¹² | | | | | | | | | | | | | | |

Study Flow Chart Footnotes:

- 1 All cohorts will complete only 1 Treatment Period.
- 2 Participants will be in the clinical unit for their in-house period from the morning before dosing (Day -1), until the completion of all the assessments on Post-Treatment 3 (Day 4).
- 3 Eligibility will be determined during screening. Continued eligibility will be confirmed on Day -1, and pre-dose Day 1.
- 4 Height measured at Screening only.
- 5 A urine sample will be used to screen for drugs of abuse (including alcohol and cotinine).
- 6 Total serum testosterone only required at screening.
- 7 Coagulation testing aPTT and PT
- 8 Vital signs include the following assessments: supine systolic and diastolic blood pressure, supine heart rate, respiration rate and oral temperature
- 9 12-lead ECG will be performed at screening, each period pre-dose and at 30 min, 4 h, 12 h, 24 h, 48 h and 72 h post-dose and at the post-study follow up visit.
- 10 IMP or placebo will be administered orally in a fasted state (after an overnight fast of at least 10 h) with 240 mL water. The fast will be broken 4 h post-dose with lunch.
- 11 Symptom directed

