10.9.18 Laboratory Safety Assessments

Laboratory Safety Screen

Laboratory safety screen samples will be analysed by Simbec-Orion Laboratory Services. Printed laboratory test result reports will include normal reference ranges. A decision regarding whether the laboratory test result outside the normal reference range is of clinical significance or not shall be made by an Investigator/designee and the report will be annotated accordingly. Clinically significant laboratory test result abnormalities will be recorded on the AE page. The normal reference ranges for laboratory test parameters will be detailed in the SLPDoc0024 Normal Reference Ranges and Alert Reference Values document.

Biochemistry Tests: Alanine transaminase (ALT), albumin, alkaline phosphatase (ALP), aspartate transaminase (AST), bicarbonate, total bilirubin, direct bilirubin (if total bilirubin is raised), calcium (Ca), chloride (Cl) c-reactive protein (CRP), creatine kinase (CK), creatinine, glucose (fasting or random), gamma glutamyltransferase (GGT), potassium (K), total protein, sodium (Na), urea, total serum testosterone and luteinizing hormone (LH).

Blood samples for biochemistry analyses for each time-point will be collected into an appropriately sized serum collection tube with or without a separator, and analysed by Simbec-Orion Laboratory Services, or at an appropriate referral laboratory, using an appropriate analyser/method(s) of analyses. Assessments of blood sample quality (i.e., for sample verification) will be performed by measuring 3 indices [namely, Lipaemic (for Lipaemia), Haemolytic (for Haemolysis) and Icteric (for Icterus)] in serum.

Haematology Tests: Haemoglobin (Hb), haematocrit, mean corpuscular volume (MCV), mean corpuscular haemoglobin (MCH), mean corpuscular haemoglobin concentration (MCHC), platelet count, red blood cell count (RBC), red blood cell distribution width (RDW), white blood cell count (WBC), and WBC differential count (neutrophils, lymphocytes, monocytes, eosinophils, and basophils) (reported in absolute and percentage values).

Blood samples for haematology analyses for each time-point will be collected into an appropriately sized blood collection tube containing ethylenediaminetetraacetic acid (EDTA) and analysed by Simbec-Orion Laboratory Services, or at an appropriate referral laboratory, using an appropriate analyser/method(s) of analyses.

Coagulation Tests: Activated partial thromboplastin time (aPTT) and prothrombin time (PT)

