10.9.20 Appropriateness of Measurements

All measurements performed in the study are standard measurements.

The total volume of blood to be collected from each participant during each part of the study will not exceed 500 mL and is considered acceptable ([Table 10.9.4](#), [Table 10.9.5](#), [Table 10.9.6](#)).

Table 10.9.4 Part A (Single Ascending Dose) Summary of Blood Volume

| Procedure | Visit | Number of Samples | Blood Volume per Sample (mL) | No. Treatment Periods | Blood Volume (mL) |
|---|------------------|-------------------|------------------------------|-----------------------|-------------------|
| Biochemistry¹ | Screening | 1 | 4.5 | N/A | 4.5 |
| | Treatment Period | 4 | 4.5 | 1 | 18.0 |
| Haematology | Screening | 1 | 3.0 | N/A | 3.0 |
| | Treatment Period | 4 | 3.0 | 1 | 12.0 |
| Coagulation | Screening | 1 | 2.7 | N/A | 2.7 |
| | Treatment Period | 4 | 2.7 | 1 | 10.8 |
| PK Drug Conc. Measurement – AX-158 | Treatment Period | 14 | 4.0 | 1 | 56.0 |
| Exploratory PD samples | Treatment Period | 2 | 2.7 | 1 | 5.4 |
| Total Blood Volume ² | | | | | 112.4 |

Footnotes:

| | |
|----------|--|
| 1 | The biochemistry blood sample collected at the Screening visit will also be used to complete the virology screen (HBsAg, HCV Ab, and HIV). |
| 2 | Please note: This total blood volume does not include any additional blood sample collection(s) for retest, unscheduled testing or additional tests required at the discretion of the Investigator/designee. The exact volumes of each sample may change but the total volume of blood drawn for any participant will not exceed 500 mL. |

Table 10.9.5 Part B (Food Effect) Summary of Blood Volume

| Procedure | Visit | Number of Samples | Blood Volume per Sample (mL) | No. Treatment Periods | Blood Volume (mL) |
|---|------------------|-------------------|------------------------------|-----------------------|-------------------|
| Biochemistry¹ | Screening | 1 | 4.5 | N/A | 4.5 |
| | Treatment Period | 3 | 4.5 | 2 (+follow up) | 31.5 |
| Haematology | Screening | 1 | 3.0 | N/A | 3.0 |
| | Treatment Period | 3 | 3.0 | 2(+follow up) | 21 |
| Coagulation | Screening | 1 | 2.7 | N/A | 2.7 |
| | Treatment Period | 3 | 2.7 | 2(+follow up) | 18.9 |
| PK Drug Conc. Measurement – AX-158 | Treatment Period | 14 | 4.0 | 2 | 112 |
| Total Blood Volume ² | | | | | 193.6 |

Footnotes:

| | |
|----------|--|

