9.2 EXTERNAL DATA

9.2.1 Laboratory Data

Transfers of safety laboratory data will be provided by Simbec-Orion Laboratory Services, delivered to Simbec-Orion Data Management via electronic transfer and stored within the study database and subsequently, within the appropriate SDTM and ADaM domains.. Details of laboratory data are documented in the Data Management Plan (DMP). Populated test transfers will be received before programming can start.

The following results will be included:

- **Hematology:** Hemoglobin, hematocrit, mean corpuscular volume, mean corpuscular hemoglobin, mean corpuscular hemoglobin concentration, platelet count, red blood cell count, red blood cell distribution width, white blood cell count and WBC differential count (neutrophils, lymphocytes, monocytes, eosinophils, and basophils) (reported in absolute and percentage values).
- **Biochemistry:** Alanine transaminase, albumin, alkaline phosphatase, aspartate transaminase, bicarbonate, total bilirubin, direct bilirubin (if total bilirubin is raised), calcium, chloride, c-reactive protein, creatine kinase, creatinine, glucose (random), gamma glutamyltransferase, potassium, total protein, sodium, urea, total serum testosterone and luteinizing hormone.
- **Urinalysis:** Bilirubin, blood, glucose, ketones [or ketone bodies], leucocytes, nitrite, pH, protein, specific gravity, and urobilinogen.
- **Coagulation:** International normalized ratio, Activated partial thromboplastin time and prothrombin time.
- **Microscopy:** In the event that the urinalysis 'dipstick' test result is positive for nitrite and/or 2+ or more reported for protein, blood, and/or leucocytes, the following test parameters will be reported microscopically: bacteria, casts (non-pathogenic), casts (pathogenic), crystals, epithelial cells, red blood cells and white blood cells
- **Virology:** HBsAg, HCV Ab and HIV test (antibodies to HIV-1 and HIV-2).
- **COVID-19 Test:** A nasopharyngeal and/or oropharyngeal swab will be collected. COVID-19 testing will be routinely performed via lateral flow test (LFT) however, a RT-PCR test may be performed at the PI's discretion.
- **Drugs of Abuse Screen and Alcohol:** alcohol, amphetamines, barbiturates, benzodiazepines, cannabinoids/tetrahydrocannabinoids (THC), cocaine, cotinine, methadone, and opiates.

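### A liver stopping criterion in protocol V4.0 uses INR >1.5, but the coagulation panel and flow charts list only aPTT and PT and do not require INR to be reported or derived

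*Protocol*

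**What the plan says.** Protocol section 10.3.4 lists criteria that stop further dosing or escalation while the data are evaluated. Once any is met, escalation resumes only after a substantial amendment is approved. Two of the criteria concern the liver. For both, the elevation must be possibly related to the product, other causes must be excluded, and the finding has "to be confirmed on repeat samples". The first reads "ALT or AST >3x ULN and (BIL-T >2x ULN or INR >1.5", with the bracket closing there. The second combines the same transaminase elevation with listed symptoms or eosinophilia.

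Section 10.9.18 of the protocol defines the coagulation tests as "Activated partial thromboplastin time (aPTT) and prothrombin time (PT" and names nothing else. Footnote 7 to Table 10.9.1, footnote 7 to Table 10.9.2 and footnote 5 to Table 10.9.3 each say "Coagulation testing aPTT and PT". Outside section 10.3.4, INR appears in the supplied protocol text only in the abbreviation list, as "international normalised ratio".

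SAP section 9.2.1 gives the coagulation data as "International normalized ratio, Activated partial thromboplastin time and prothrombin time". The corresponding footnotes to the three schedules in SAP section 3.4.1 also add INR. SAP section 1.1 says the plan was written from protocol V5.0 of 15 March 2022. The protocol supplied is V4.0 of 14 January 2022.

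**The concern.** This is a first-in-human study, and the first liver criterion is written as an objective laboratory rule. Each quantity in such a rule should be one the protocol requires to be reported. On V4.0 as written, INR is not.

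Two things are at stake.

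- **Applying the rule.** Take a participant with confirmed ALT or AST above 3x ULN and impaired clotting, but with bilirubin at or below 2x ULN and none of the listed symptoms or eosinophilia. On the results that V4.0 requires, this participant meets neither liver criterion. Escalation decisions rest on a summary of laboratory assessments (protocol section 10.3.1), supplied as listings of the clinical database (SAP section 7). Nothing in V4.0 requires INR to be in that database.
- **Completeness of the safety tables.** The SAP treats INR as a coagulation parameter throughout Part A, summarises each laboratory parameter by treatment and time point (section 11.6.2), and uses no method for missing safety data (section 10.4). If INR was not reported in cohorts tested under the aPTT/PT panel, the coagulation tables would have gaps there.

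**Working it through.** No power or sample-size arithmetic applies. The check sets the criterion beside the tests.

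**Step 1: inputs to the two liver criteria, and where each is listed.**

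| Quantity | Used in | Protocol V4.0 section 10.9.18 | SAP section 9.2.1 |
|---|---|---|---|
| ALT, AST | both criteria | biochemistry | biochemistry |
| Total bilirubin | first criterion | biochemistry | biochemistry |
| INR | first criterion | not listed | coagulation |
| Eosinophils | second criterion | haematology | haematology |

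The symptoms in the second criterion come from adverse event recording. INR is the only laboratory input that V4.0 does not list.

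**Step 2: places that define coagulation testing.**

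- Protocol: section 10.9.18 plus three flow-chart footnotes = 4 places, of which 0 include INR.
- SAP: section 9.2.1 plus three schedule footnotes = 4 places, of which 4 include INR.

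**Step 3: scheduled coagulation samples per participant (protocol Tables 10.9.4 to 10.9.6).**

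- Part A: 1 + 4 = 5.
- Part B: 1 + (3 × 2 + 1) = 8. The volume agrees: 18.9 / 2.7 = 7 samples after screening.
- Part C: 1 + 7 = 8.

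PT is specified for every one of these samples and INR for none. The blood is therefore drawn, and what V4.0 lacks is a requirement to report INR or derive it.

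**Step 4: which participants could be affected.** The amendment assessment form appended to the protocol says that Part A was ongoing while V3.0 was the approved version, and that review of the Cohort 2 PK data was still to come. At least the earliest Part A participants were therefore tested before V5.0. The protocol's revision history records no change to the coagulation panel up to V4.0, so nothing suggests that earlier versions listed INR.

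**Step 5: what can be said about V5.0.** SAP section 1.2 names two departures from the protocol (a PK Set criterion and the Part B model), neither about laboratory tests. The SAP schedules also differ from V4.0 in other ways. The mid-dosing safety tests in Part C are pre-dose on Day 5 rather than Day 7, and Part B gains a pre-dose testosterone test. This pattern suggests that V5.0 revised the schedules and may have added INR. It does not prove it.

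**The case against.** The strongest case on the other side has four parts.

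1. INR is a standardised form of PT, and PT is scheduled in every part, so the laboratory could report INR from the same tube.
2. The criterion itself calls for repeat samples, and the footnotes to the blood-volume tables foresee "unscheduled testing or additional tests required at the discretion of the Investigator/designee".
3. Other stopping routes remain. Section 10.3.4 also covers a severe adverse event in a key safety variable, expressly including laboratory safety, and any other toxicity judged to preclude dosing. Section 10.3.3 adds general discontinuation, and clinically significant laboratory abnormalities are recorded as adverse events.
4. The SAP lists INR in the same four kinds of place, so V5.0 has probably dealt with the matter, and the difference between the documents may only be one of version.

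All four stand as limits on the size of the problem. A reader might infer that the INR part of the rule cannot be applied at all, or that a participant with liver injury and impaired clotting would go unstopped. The documents support neither reading, for the first three reasons. A reader might also infer that INR is certainly missing from the SAP tables for early Part A cohorts. That is not shown either, because neither document says what the laboratory reported alongside PT.

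What the objection does not do is supply the missing requirement. V4.0 states no PT value that corresponds to the INR limit and does not say that INR will be derived. Discretionary tests are not specified inputs to a rule. The remaining routes rest on the opinion of the investigator or the sponsor, whereas this one was written to be objective. A correction in V5.0 would not by itself supply INR for cohorts already tested.

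**Conclusion.** Protocol V4.0 contradicts itself on this point. A binding stopping criterion depends on INR, and none of the four places that define coagulation testing requires INR to be reported or derived. The size is modest: one of two laboratory routes into one of two liver criteria. The bilirubin route and the second liver criterion are unaffected. It is still worth correcting, because it concerns a safety rule and the correction is cheap.

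The conclusion rests on three assumptions.

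- The supplied V4.0 text is complete on laboratory tests.
- INR can be obtained from PT. This is general laboratory knowledge, which neither document describes, and it needs laboratory-specific calibration values that neither document gives.
- V5.0 was not available. If it lists INR, the contradiction is closed from that version on, and only the question of early cohorts remains.

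**What to change.** **Protocol.** Reconcile section 10.3.4 with section 10.9.18 and the footnotes to Tables 10.9.1, 10.9.2 and 10.9.3, so that the quantity in the criterion is one the panel is required to report. Listing INR with PT, as the SAP does, is one way. If V5.0 already does this, confirm it and no further protocol change is needed. No threshold or clinical rule is proposed here.

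**Cohorts tested under the aPTT/PT panel.** Confirm with the laboratory whether INR was reported. If it was not, obtain it from the laboratory's PT data where its calibration values allow, or state in the SAP coagulation tables that INR is unavailable for those cohorts. Values obtained afterwards complete the tables but cannot alter escalation decisions already taken.

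**Cost.** One line in section 10.9.18 and three footnotes, with no extra blood sample or visit. For the early cohorts, one query to the laboratory and then either a retrospective calculation or a table footnote.
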